1. GLOSSARY OF ABBREVIATIONS

AE	Adverse Event
APR	Annual Progress Report
AR	Adverse Reaction
CI	Chief Investigator
CRF	Case Report Form
ED	Emergency Department
EVW	Episodic Viral Wheeze
FeNO	Fractional Exhaled Nitric Oxide
GCP	Good Clinical Practice
GDPR	General Data Protection Regulation
GP	General Practitioner
HRA	Health Research Authority
ICF	Informed Consent Form
ICS	Inhaled Corticosteroids
ID	Identification Number
IL	Interleukin
LPLV	Last Patient Last Visit
MHRA	Medicines and Healthcare Products Regulatory Agency
MTW	Multiple-Trigger Wheeze
Non-CTIMP	Non-Clinical Trial of an Investigational Medicinal Product
OCS	Oral Corticosteroids
PI	Principal Investigator
PIS	Patient Information Sheet
REC	Research Ethics Committee
R&D	Research and Development
RGF	Research Governance Framework
SAE	Serious Adverse Event
SMF	Study Master File
SOP	Standard Operating Procedure
SPTs	Skin Prick Tests

KEYWORDS:

Wheezing, preschool, children, atopic sensitisation, atopy, aeroallergens, blood eosinophils, eosinophilia, FeNO.

2. STUDY SUMMARY

TITLE: Biomarkers in preschool children with wheeze to Target therapy with inhaled corticosteroids (TAILOR): a feasibility study”.

AIM: To obtain pilot data to test the hypothesis that aeroallergen sensitisation (confirmed by a wheal formation with a diameter ≥ 3 mm after a skin prick test is performed), FeNO (offline method) ≥ 10 ppb and a peripheral blood eosinophil count $\geq 300/\mu\text{l}$, alone or in combination, can predict future wheezing exacerbations in preschool children as well as response to treatment with inhaled corticosteroids, as a preliminary to a large, randomised controlled trial. Also, that these tests are acceptable to families.

OBJECTIVES:

- To recruit 100 preschool children with a history of wheeze, aged one to five years old, and determine atopic status, peripheral blood eosinophil count (point of care test) and FeNO (offline method).
- To evaluate the feasibility and acceptability of these tests
- To categorize the children according to the biomarkers tested and assess whether any or all, alone or in combination, predict future wheezing exacerbations as well as determine the clinical outcome over one year
- To obtain parents' and doctors' insights into whether the biomarkers mentioned above could be used in a future intervention study.

OUTCOME Primary outcome:

- MEASURES:**
- Acute attacks of wheeze defined as requiring an unscheduled health care visit

Secondary outcomes:

- Carer days off work
- Children unable to attend childcare facility
- Use of oral corticosteroids
- Use of inhaled β -2 agonist (rescue therapy)
- Assessment if children's respiratory or wheezing condition is under control by using the TRACK™ score questionnaire (Test for Respiratory and Asthma Control in Kids) (Appendix 3).

POPULATION: Children aged one to five years old presenting either to primary care with wheezing episodes or to emergency departments with an acute attack of wheeze or to secondary care (e.g., outpatients) or children identified from primary care records and have been diagnosed with wheezing by their GP or paediatrician.

ELIGIBILITY: (children)	Inclusion criteria: 
1. Patients aged one to five years old presenting either to primary care or to the emergency department or to secondary care (e.g., outpatients) or identified from primary care records and have been diagnosed with wheezing by their GP or paediatrician who has decided to prescribe any bronchodilator, ICS or montelukast on clinical grounds2. Parents/Carers able to understand and familiarize themselves with the study and are willing to provide informed consent Exclusion criteria: 
1. Inability to understand and cooperate with study procedures2. Significant co-morbidity (respiratory or otherwise), for example cystic fibrosis (excluding atopic disorders such as eczema, allergic rhinitis and food allergy)3. Withholding or withdrawal of informed consent4. Severe procedural anxiety (needle phobia)5. Child is already enrolled in another study involving investigational medicinal product (CTIMP)6. History of anaphylaxis or near-fatal asthma that resulted in intubation / assisted ventilation.
ELIGIBILITY: (Healthcare professionals)	Inclusion Criteria: 
1. Doctors and nurses working in GP practices. Exclusion Criteria: 
1. Inability to understand and cooperate with study procedures.
DESIGN:	This is a pragmatic, observational study in children with pre-school wheeze. After recruitment and at the first study visit, biomarkers (allergic sensitisation, exhaled nitric oxide and peripheral blood eosinophil count) will be measured. The children will be followed for a year, with monthly electronic questionnaires and study visits every 3 months. All treatment and routine monitoring decisions will be at the discretion of the children's general practitioner (GP) or paediatrician (as per usual clinical practice), blinded to the study measurements. There will be a second optional biomarker measurement 3 months after the first one, in their second study visit. Parents/Carers of preschool children presenting either to primary care or to the Emergency Department (ED) or to secondary care (e.g., outpatients) as well as of those identified from primary care records and have been diagnosed by their GP or paediatrician with wheezing, will be identified by collaborating doctors and nurses who will ask the parents if they are willing to have their child participate in the study (the list of recruitment sites is given in Appendix 1 – Recruitment Plan). A patient information sheet will be given, containing all the information regarding the

[figure not shown]
project and the contact details of the research team, for further questions. They will be asked for their willingness to give the study team permission to contact them and discuss recruitment. After clinical consultation and following submission of the electronic informed consent, the parent/carer will be asked to give the contact details of the child's GP or paediatrician, who will be informed about child's participation in this study through a letter sent to his/her email along with the patient information sheet. In addition, we will ask them to provide some of the child's personal data. The parent carer will be then shown a standard video questionnaire and will be asked to identify what respiratory sounds their children have been making. The child will be booked for the above biomarker tests at a single visit and at a time of clinical stability. If the child has been prescribed OCS, biomarker testing will be delayed by 2 weeks. Firstly, a sample of the child's exhaled tidal breath will be collected in a suitable bag for offline measurement of FeNO. Skin prick tests will be performed to (a) house dust mite, (b) grass pollen, (c) tree pollen, (d) cat hair € dog hair, as well as negative and positive controls and these will be applied on either the child's back, leg or arm. If the child has been prescribed antihistamines, we will ask for these to be withheld for 72 hours prior to skin prick testing. Finally, the peripheral blood eosinophil count will be measured from a finger prick blood sample, using the Haemocue machine, giving a result in approximately 2 minutes. All tests will normally take no more than one hour.

[figure not shown]
Follow-up: We will arrange for a short monthly electronic questionnaire to be sent by email to the parents/carers, to record on a monthly basis, the days their child was out of childcare, days the carer missed from work, unscheduled health care visits and use of rescue therapy or oral corticosteroids (including dosage) (Appendix 4: Monthly Questionnaire). We will record the children's TRACK™ score (Test for Respiratory and Asthma Control in Kids) (Appendix 3: TRACK™ score questionnaire) every 3 months to assess wheeze control. In addition, review visits will occur every 3 months, but if not feasible, video calls will be arranged through Microsoft Teams. Correct inhaler use will be ensured by parental education. If a child has had their ICS treatment discontinued, we will record whether this was because the treatment was ineffective (treatment failure) or if the child was so well that the family or GP did not wish to continue (treatment success or spontaneous improvement). If an additional medication is prescribed, or the child is referred to secondary care, this will be considered as treatment failure. When the study ends, parents/carers will be given the opportunity to join a focus group and give their insights into the investigations and the conduct of the study and inform the design of the future intervention study. In addition, we will ask them to fill in a very short questionnaire after the study is finished, to check their perspective

and acceptability on these biomarkers being used in clinical settings to guide children's therapy in the future (Appendix 5: Exit Questionnaire). Finally, a focus group for doctors and nurses will also be conducted to check the feasibility of the 3 biomarker tests being used in clinical practice.

DURATION: 36 months total study duration, with 1-year follow-up for each child participant included. Study's start date will be 01.09.2021 and end date will be 31.12.2023.

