4.3. PRE-CLINICAL/CLINICAL DATA

This highly variable pathophysiology of pre-school wheeze is reflected in the response to treatment, making the determination of phenotype much more than a matter of academic importance. In the first serious attempt to apply personalised medicine to this group of patients, the INFANT study investigators used a three way crossover design to compare the differential response to therapy with intermittent ICS, regular ICS and montelukast in 300 children (15). Sixty improved spontaneously over the duration of the study. Atopic sensitisation predicted a good response to ICS, shown by reduced numbers of attacks of wheeze and better control of chronic symptoms. In a retrospective analysis, an elevated blood eosinophil count and even better, a combination of positive SPTs and peripheral blood eosinophils $>300/\mu\text{l}$ were the best predictors of a good response to regular ICS. Leukotriene receptor antagonists were not beneficial in any group. Those with no positive SPTs or elevated eosinophil count rarely had acute attacks of wheeze. These findings, especially the predictive power of blood eosinophil count, need to be tested prospectively in primary care, the setting in which most of these children are treated, in a large prospective randomised controlled trial. Prior to this, pilot data to inform power calculations, and the feasibility and

acceptability of this approach needs to be determined. Additionally, although FeNO in preschool children is not well standardized there is one study which proposed FeNO values ≥ 10 ppb to be predictive of eosinophil inflammation in preschool children (16).

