The recruitment period will approximately last 9 months, and all preschool wheezers can join the study at any point (Appendix 1: Recruitment Plan). Parents/Carers of preschool children presenting to primary care or to the Emergency Department (ED) or to secondary care (e.g., outpatients) as well as those identified from primary care records and who have been diagnosed by a GP or paediatrician with wheezing, will be approached by collaborating doctors and nurses who will ask their parents if they are willing to have their child participate in the study (Appendix 1: Recruitment Plan). A patient information sheet will be given, containing all the information regarding the project and the contact details of the research team, for further questions. They will be asked for their willingness to give the study team permission to contact them and discuss recruitment, and if so, they will submit their contact details in an electronic form made with Qualtrics® questionnaire platform (offered by Imperial College London), which allows gathering data according to the GCP guidelines and as used for years in the Breathing Together study (19). This form will be available online in the Asthma UK Centre for Applied Research's (AUKCAR) website. The initial introduction

will be made either by the clinical team (above) with the study team contacting them at a later date to give more information or by [name] if he is there in person.

Additionally, the Emergency Department of Oxford Universities Hospital (OUH) Trust will identify patients who have previously presented and diagnosed with wheezing in the Emergency Department. A regular search of the OUH databases will be performed by the clinical care team to identify patients who meet the eligibility criteria and have attended the Emergency Department. Parents/carers of eligible participants will be informed about the study by phone by a member of their clinical care team and asked whether they agree to be contacted by the study team to give them more information and send them the participant information sheet. Their contact details will be then submitted in the TAILOR study contact details form.

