In the event that a child has had their ICS treatment discontinued, we will record whether this was because the treatment was ineffective (treatment failure) or if the child was so well that the family or GP did not wish to continue (treatment success or spontaneous improvement). If an additional medication is prescribed, or the child is referred to secondary care, this will be considered as treatment failure. When the study ends, participants' parents/carers will be invited to a face-to-face focus group interview, or a one-to-one interviews, or remotely through Microsoft Teams, depending on their availability at the end of the study period. The focus group and one to one interviews will utilise a semi structured questionnaire, to provide qualitative feedback on the acceptability of the 3 biomarker tests. In addition, a separate focus group for doctors and nurses will be conducted to assess the feasibility of the 3 biomarker tests being used in clinical practice. They will be given all the information regarding the study as well as the study's patient information sheet. Those agreeing to take part, will sign a consent form. They will be attending either a face-to-face focus group interview, or a one-to-one interview, or remotely through Microsoft Teams, depending on their availability. A semi structured questionnaire will be utilised. Where possible a second independent researcher will sit in the focus groups discussion and interviews to ensure there is no bias. The conversations from the focus group and one to one interviews will be transcribed and coded into themes. We will utilise an external company for transcribing the conversations called 1st Class. <https://www.1stclass.uk.com/>

The focus group and one to one interviews will be audio recorded, transcribed and put into themes to conduct an inductive thematic analysis. 25% of the transcripts will be

double coded by an independent researcher, experienced in qualitative research to ensure that the correct themes have been used and to ensure that there is no bias. The focus group and one to one interviews will be used to assess the acceptability and feasibility of measuring biomarkers in primary care and using them to help determine management of preschool wheeze.

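### Hospital and primary-care recruits are pooled with no analysis by route, so the pilot's attack rate may not carry over to the primary-care trial it is meant to size, and marker comparisons may be confounded by route

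*Combined protocol and SAP*

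**What the plan says.** The recruitment objective is "To recruit 100 preschool children with a history of wheeze, aged one to five years old". The Study Summary and section 7.2.1 admit children who present to primary care, to the emergency department (ED) or to secondary care, and children found in primary care records. The Population entry describes the hospital and records routes as "to emergency departments with an acute attack of wheeze or to secondary care (e.g., outpatients) or children identified from primary care records". Section 6 adds a further hospital route for children who attended the ED earlier: "A regular search of the OUH databases will be performed by the clinical care team". Entry is open ("all preschool wheezers can join the study at any point"), and no quota or target by route is given. Table 1 in Appendix 1 lists a hospital trust beside GP practices, without numbers.

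Section 4.3 says the earlier findings "need to be tested prospectively in primary care, the setting in which most of these children are treated, in a large prospective randomised controlled trial", and continues: "Prior to this, pilot data to inform power calculations", together with evidence on feasibility and acceptability, is required.

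Section 6.1 makes the primary outcome attacks of wheeze that lead to an unscheduled visit. Section 11 lists chi-squared, Fisher's exact, Student t and Mann-Whitney tests at p<0.05. It plans no stratification, covariate, regression or summary by recruitment route.

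**The concern.** The pilot is meant to supply planning figures for one population, but its only planned estimates come from a mixture whose composition is left to chance. Children who enter through the ED are selected by an event of the same kind as the primary outcome, so they may well go on to have more attacks than children found in GP records. If they do, a trial sized on the pooled rate expects more events than primary care will yield and ends up underpowered.

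The second issue concerns the objective of testing whether the markers predict attacks. If hospital-recruited children have more attacks and are also more often marker-positive, a marker that predicts nothing within either setting will look predictive in the pooled data. None of the listed tests would separate the two explanations.

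**Working it through.** **What can be reproduced.** The documents give no attack rate, effect size, power, expected mix or marker prevalence by route, and no derivation of the 100 children. There is no figure to reproduce, so everything below is illustration.

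**Inputs.** From the documents: 12 months of follow-up per child and a significance level of 0.05 (sidedness not stated; two-sided assumed). Assumed: hospital share s = 30, 50 or 70%; hospital rate h = 1.6 or 2.0 attacks a year; primary-care rate p = 0.8 or 1.0; within-route negative binomial dispersion 1; future-trial rate ratio 0.7; 80% power.

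**Formulas.**
- Pooled rate: m = s·h + (1−s)·p.
- Children per arm at control rate m and dispersion k: n = (1.960 + 0.842)² × [1/m + 1/(0.7m) + 2k] / (ln 0.7)², where (1.960 + 0.842)² = 7.849 and (ln 0.7)² = 0.1272.
- True power in primary care: Φ(|ln 0.7| / √([1/p + 1/(0.7p) + 2]/n) − 1.960).
- Dispersion of the mixture when each route has dispersion 1: k* = [2(s·h² + (1−s)·p²) − m²] / m².

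**Central case (s = 50%, h = 2.0, p = 0.8).**
- m = 0.5×2.0 + 0.5×0.8 = 1.4.
- Sized on 1.4 with k = 1: 7.849 × (0.714 + 1.020 + 2)/0.1272 ≈ 230 per arm.
- Needed at 0.8: 7.849 × (1.250 + 1.786 + 2)/0.1272 ≈ 311 per arm.
- Shortfall: 1 − 230/311 = 26%. Power: Φ(0.357/0.148 − 1.960) ≈ 67%.
- Mixing rates also inflates the dispersion: k* = (2×2.32 − 1.96)/1.96 = 1.37. A planner who takes both rate and dispersion from the pooled pilot gets 7.849 × (1.735 + 2.735)/0.1272 ≈ 276 per arm: 11% short, 75% power.

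**Range over the assumed grid.**

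| Planning basis | Too few children | True power |
|---|---|---|
| Pooled rate, dispersion fixed at 1 | 8% (s 30%, h 1.6, p 1.0) to 31% (s 70%, h 2.0, p 0.8) | 76% to 64% |
| Pooled rate and pooled dispersion | 1% (s 30%, h 2.0, p 0.8) to 22% (s 70%, h 2.0, p 0.8) | 80% to 70% |

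**Cross-check on a binary outcome.** Assume a one-year attack risk of 40% in primary care and 60% in hospital recruits, half from each, and a 30% relative reduction. A trial sized on the pooled 50% needs 340 children in total; sized on 40% it needs 488. The 340-child trial has about 65% power at 40%. If hospital recruits had the lower risk (30% against 40%), the pooled 35% would call for 594 children against 488, so the trial would be too large.

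**Confounding.** Assume 40-50% of hospital and 20-25% of primary-care children are marker-positive, with no marker effect within either route. The crude rate ratio is the route-weighted mean rate in marker-positive children divided by that in marker-negative children.
- Smallest (s 70%, h 1.6, p 1.0, prevalence 40% and 25%): 1.473/1.391 = 1.06.
- Largest (s 30%, h 2.0, p 0.8, prevalence 50% and 20%): 1.421/1.054 = 1.35.
- If either the attack rate or the marker prevalence is equal across routes, the ratio is exactly 1.

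**The case against.** The strongest reply is that this is a pragmatic feasibility study, that broad entry is deliberate, and that section 11 describes its tests only as those currently planned. Route of identification is also an imperfect stand-in for setting: ED attenders and outpatients have GPs too, and the database search finds children who attended earlier, not only those in an attack. With 100 children, splitting by route costs precision, and a null-marker ratio near 1.06 is small beside sampling error. All of this stands. It limits how firmly results by route can be read. It does not explain why the mix should go unreported when the planned trial is set in primary care.

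A reader might infer more than the documents support:
- **That the pooled rate is too high, or that marker comparisons are confounded, as established facts.** No rates, mix or prevalences by route are given. The effects vanish if routes are alike, and the rate bias could reverse.
- **That route is not recorded.** Table 3 of Appendix 1, which lists the personal data collected, was not in the text available for this review. Only the absence of a planned analysis by route can be stated.
- **That the treatment-failure rule adds to the problem.** Section 6 says that if an additional medication is prescribed, "or the child is referred to secondary care, this will be considered as treatment failure". The referral part may work differently for a child already under outpatients. But treatment failure is not an outcome listed in section 6.1, and the additional-medication part applies on every route. It is a side issue.

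**Conclusion.** The gap is real, in conditional form. The plan pools routes, intends the data to help size a primary-care trial, and states no analysis by route. An upward bias in the base rate is plausible, but neither its size nor its direction can be taken from the documents.

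The size depends on how the future trial is planned. The larger shortfalls arise only if the planner takes the rate from the pilot and fixes dispersion at 1. Using the pilot's own pooled dispersion recovers part of the loss, because the mixing that raises the rate also raises the dispersion. Both ranges rest entirely on the assumed rates, shares, rate ratio and within-route dispersion. The confounding range also rests on the assumed marker prevalences. This is an inexpensive improvement to the analysis and no reason to change recruitment.

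**What to change.** 1. Confirm that recruitment route is recorded for each child; add the field if it is not.
2. Report attack rate and dispersion with 95% confidence intervals, and marker prevalence, separately for hospital-recruited and primary-care-recruited children.
3. For the main marker-attack analyses, add an exploratory route-stratified or route-adjusted estimate, for example Mantel-Haenszel or negative binomial regression. Not every comparison needs it.
4. State that the trial's power calculation will take its base rate from the primary-care children, with the pooled estimate as a sensitivity case.

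The cost is at most one data field, one table and a method that section 11 does not yet list. Recruitment and the burden on children do not change. The downside is precision: for a risk near 50%, the 95% half-width is 1.96 × √(0.25/n), about ±14 points with 50 children against ±10 with 100.
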